3.4 Randomization and blinding

Six participating hospitals have been divided into 3 pairs based on the geographical location and convenience for conducting the surveys. The first paired hospitals include two provincial hospitals from the north of Laos (Luang Namtha and Xiengkhuang), the second pair includes hospitals in the center (Mahosot Hospital-central referral hospital and Vientiane provincial hospital which is 80 km from the center of the capital to the north). The third pair includes two provincial hospitals from the south of Laos (Savannakhet and Salavan).

As there are only 3 orders to be assigned, clusters will be randomly assigned to one of three start dates using a simple random sampling, to have access to the study intervention. Three paired hospitals (LNT+XK, MS+VTP and SVK+SV) will be written on three different paper slips (similar paper size and paper texture). All slips will be folded to the same size and put in the non-transparent container, covered firmly and mixed well. A person who is not related to the study will be asked to pick up the paper slip one by one and read out to the PI and a co-investigator. Simple random sampling processes will be performed before the start of the project and the order of each paired hospital to intervention introduction will be recorded. At month 4 after the start of the project, the intervention will be introduced to the first selected paired hospital, then every four months each pair of hospitals will be rolled out from the reference phase to the intervention phase until all have started the intervention. This will give 1:1 ratio of intervention vs reference period of observation (figure 2). We will therefore be able to compare the effects of the reference and intervention over a reasonable period of time. Neither hospitals nor investigators will be blinded to the introduction of the intervention.

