3.5 Study intervention and reference

Before starting the project, PI, co-investigators and research team will visit each participating hospital to discuss about the project's objectives and how we would like to conduct this project during 16 months to the directors of the hospitals. These six hospitals have already participated in Global PPS, led by the PI and research team of this project. Hospital staff will be informed about the study by the PI and a director of hospital (also co-investigator) before starting the project and all prescribers in participating hospitals will be encouraged to participate in the training and surveys.

a. Pre-study phase

Four participating hospitals (MS, XK, LNT and SV) in this study have already participated in Global-PPS since 2017, whilst VTP participated in 2018 and SVK in 2019. Antimicrobial prescription data of all six hospitals are available for the whole of 2019. This is the period when there were no available Lao therapeutic and prophylactic antimicrobial prescribing guidelines. These data will be used in this project to compare the change in proportion of antimicrobial prescriptions and the change in administration route before and after the introduction of the prescribing guidelines (both paper-based and mobile phone app versions). To be able to answer our study question, Lao therapeutic and prophylactic antimicrobial prescribing guidelines were developed to be introduced at month 0 of the project. Details of Lao therapeutic and prophylactic antimicrobial prescribing guidelines are described below.

Lao antimicrobial prescribing guidelines

Lao National antimicrobial prescribing guidelines are based on existing Lao treatment guidelines, current data on infectious disease pathogens and antimicrobial susceptibility patterns in Laos and international antimicrobial prescribing/treatment guidelines (e.g. WHO, CDC, NICE, ISID, Sanford). The guidelines are separated into paediatric and adult guidelines for ease of use. These guidelines include recommendation for therapy, prevention and antibiotic stewardship.

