1. Mahosot Hospital - 16 wards, including infectious disease paediatrics, general paediatrics, neonatal-paediatric intensive care unit (ICU), ICU adult, general medicine, gastro-intestinal, cardiovascular, infectious disease adult, lung, psychology, ear-nose-throat (ENT), abdominal surgery, uro-surgery, plastic surgery, general surgery, post operation room, obstetrics and gynaecology (OBGY)
2. LNT provincial hospital - 7 wards, including medicine, surgery, paediatrics, OBGY, intensive care unit, ENT
3. XK provincial hospital - 11 wards, including cardiology, infectious disease, OBGY, ICU adult, ICU paediatrics, surgery, post operation, medicine, eyes, and specialty ward (mixture of medicine, surgery, OBGY or paediatric patients – this ward is for patients who need private and more comfortable room)
4. VTP provincial hospital - 5 wards, including paediatrics, OBGY, medicine, surgery and ICU
5. SVK provincial hospital - 9 wards, including medicine 1, medicine 2, lung, infectious diseases (HIV/AIDs ward), surgery, OBGY, ICU and specialty ward
6. SV provincial hospital - 7 wards, including medicine 1 (general medicine), medicine 2 (mostly infectious disease patients), lung, paediatrics, surgery, OBGY and ICU

Survey dates and times – PPS will be conducted every four months throughout the year. There will be 5 PPS in total from the start of the project (month 0) until the finish date of the project (month 16) (Figure 2).

PPS must be completed within a maximum of 5 consecutive working days from the start date of collecting data in hospital of that PPS round. All hospital charts of all admitted patients on a ward must be screened at 8 o'clock in the morning on the day of the survey. Survey days will be from Monday to Friday, excluding public holidays.

Survey staff

- Research staff, *OR*

- Local doctor who is familiar with their own local hospital charts and has been trained on data collection for this project

Inclusion and exclusion criteria

Inclusion criteria

1. All patient hospital charts from all in-patient wards at 8:00 o'clock in the morning of a survey day will be counted as the denominator
2. All patient hospital charts from all in-patient wards with any kind of antimicrobial agent (s) prescribed at 8 o'clock in the morning of a survey day will be counted as numerator.

Definition for IPD surveys

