- Patients who are on topical antimicrobial agent(s) alone will be excluded from numerator but they will still be in the denominator

Survey setting

Research team will inform the hospital directors three days before starting each PPS (both IPD and OPD). Research staff will start collecting data on the ward at 8:00 o'clock in the morning of the survey day with permission of the hospital director few days before starting survey (both at IPD and OPD). The ward doctors and nurses will be informed about the survey on the same day as the survey day. Research staff will work on hospital charts only without interviewing any patients or ward staff, unless the number of charts and number of patients are not consistent or there is unclear handwriting of doctors or nurses. Research staff must complete the survey of a ward within a day. Research staff must finish a survey of one ward before moving to another ward.

If research staff cannot start the survey at 8:00 o'clock in the morning of the survey day for all wards, starting a new ward after 8:00am is acceptable with the condition of excluding all patients who are admitted to hospital after 8:00am (8:01am) of the survey day.

If some hospital charts are not available at the wards during the survey time (i.e. consulting with other medical specialties at other wards), the survey team can come back to that ward in the same day for that hospital chart but excluding all information after 8:00am of that survey day.

For more details of in-patient PPS data collection form, see **Appendix A1. In-patient PPS Ward Form** and **Appendix A2. In-patient PPS Patient Form**.

a.2 Out-patient point prevalence survey

Design – Point prevalence survey

Survey site – In most hospitals, many wards have their own OPD within their wards. In this study, we will focus on three main wards (Paediatrics, Medicine and Surgery) where we would expect that the most antimicrobial prescribing would occur.

Survey dates and times – PPS will be conducted every four months throughout the year or three times a year with 4-month intervals between each survey. There will be 5 surveys in total. PPS in OPD will be performed for 5 consecutive working days in total from the start date of collecting data in the hospital in that PPS round.

All outpatient prescriptions will be screened between 8:00 o'clock in the morning and 4:00 o'clock in the afternoon on the day of survey. Survey days should be from Monday to Friday, excluding public holiday and weekends.

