
Surveyor qualification

- Research staff, *OR*
- Local doctor who received training for data collection for this project

Inclusion and exclusion criteria

Inclusion criteria

1. All patients consulting at OPD of paediatrics, medicine and surgical wards of all participating hospitals during 8:00am and 4:00pm of a survey day will be counted as the denominator

2. All patients consult at OPD of these three wards of all participating hospitals who are prescribed antimicrobial (s) between 8:00am and 4:00pm on a survey day will be counted as the numerator
3. If the same outpatient comes back for consultation during the same survey period (same round, any day during these five days) this patient will also be included in the survey and be defined as a new consultation.

Definitions for OPD surveys

- **Denominator:** all outpatients who consult at paediatrics, medicine and surgical OPDs on the survey day between 8:00am and 4:00pm for 5 consecutive working days. Patients who come outside this period of time will be excluded from the survey
- **Numerator:** all outpatients who consult at paediatrics, medicine and surgical OPDs and are prescribed antimicrobial (s) on the survey day between 8:00am and 4:00pm for 5 consecutive working days. Patients who come outside this period of time will be excluded from the survey, even if they are prescribed any antimicrobial (s).

Exclusion criteria

- Patients who come for consultation outside the survey time (before 8:00am or after 4:00pm) of the survey day
- Patient who are prescribed topical antimicrobial (s) only will be excluded from numerator but they will still be in the denominator

Study setting

OPD PPS will be conducted for 5 consecutive working days. Hospital directors of each hospital will be informed three days before the survey. Head of OPD will be informed about the survey on the same day as they survey day. Data will be collected from an OPD prescription sheet at the OPD pharmacy. There will not be any private discussion or interview of patients or doctors.

The OPD prescription sheet from patients will be scanned and saved as an electronic file for data entry by research staff on the same day. The reason for scanning OPD prescription sheets is to avoid disrupting the OPD workflow of the rush hours of each participating hospital. The total number of OPD patients (denominator) will be collected from the OPD logbook at the end of each survey day.

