This study targets the behaviour of all prescribers rather than individuals. We will therefore focus on cluster information rather than individual data. Only prescribers' age, speciality, and the year of graduation will be collected as their personal details. Nobody (including research team and the PI of the study) will be able to identify the person who fills the survey form from a completed survey CRF or who prescribe antimicrobial (s) from ODK systems or database. All complete survey forms will be kept secured in the locked filing cabinet and all electronic data will be protected by password access.

Trial insurance

The University of Oxford has a specialist insurance policy in place: Newline Underwriting Management Ltd, at Lloyd's of London, which would operate in the event of any participant suffering harm as a result of their involvement in the research.

Data sharing and dissemination

This stepped wedge cluster randomized controlled trial will generate valuable data for healthcare sectors and for diverse further research projects in AMR field in Laos. This trial will provide data of hospital antimicrobial use across Laos, which have never been reported before. It will introduce a Lao language antimicrobial prescribing guidelines mobile app for the first time. This project will also provide data on cost of antibiotics use comparing between the paper-based and the mobile phone app prescribing guidelines. The study will also have global impact as an evaluation of an increasingly popular intervention that lacks a strong evidence base.

AMU-Laos App (computer dashboard) will be used to demonstrate real time results of the point

prevalence survey on hospital antimicrobial use at each stage to local authorities, the MoH and policy makers. AMU-Laos App can generate the report to the users with just one click.

Information on each PPS on hospital antimicrobial use will be shared with participating hospital staff and authorities and public health departments of each participating provinces, as well as MoH and funder one month after each survey.

The Lao-language antimicrobial use guidelines mobile application will be discussed with the MoH before starting the trial and only shared with doctors in participating hospitals during the trial period.

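### In-patient survey data may be abstracted by a local doctor of the surveyed hospital, with no rule on own-ward surveying or on keeping surveyor type constant across rounds

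*Combined protocol and SAP*

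**What the plan says.** Section 3.7, a.1 (Survey staff) names two kinds of in-patient surveyor: research staff, or a "Local doctor who is familiar with their own local hospital charts and has been trained on data collection for this project". Under a.2 (Surveyor qualification) the out-patient alternative is a "Local doctor who received training for data collection for this project", without mention of the doctor's own hospital.

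In-patient data are taken directly from hospital charts. Out-patient prescription sheets are scanned, and research staff enter the data from the scans.

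On notice, the a.1 Survey setting states: "The ward doctors and nurses will be informed about the survey on the same day as the survey day". The head of the out-patient department is likewise told on the day. Hospital directors are told three days ahead.

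On blinding, Section 3.4 states: "Neither hospitals nor investigators will be blinded to the introduction of the intervention". On whose prescribing is measured, the confidentiality section states: "This study targets the behaviour of all prescribers rather than individuals".

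Section 3.6 defines adherence by agent and dose against the guideline. Form A2 collects agent, dose, diagnosis and type of indication. The surveyor's name is recorded on forms A1 and A3.

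**The concern.** The guidelines, the app and the stewardship training go to the hospital's doctors generally. A local-doctor surveyor can therefore be one of the prescribers whose behaviour is the outcome, working in a hospital that knows which phase it is in. Whether a prescription matches the guideline depends on which diagnosis and indication are recorded beside it, and a doctor reading charts on his or her own ward can fill those fields from memory or favourably.

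Three things are at stake:

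- **Abstraction.** If it becomes more generous once the app has arrived, the app-versus-paper contrast moves without any change in prescribing. Masked coding of adherence afterwards would not repair a diagnosis that was recorded with bias.
- **Surveyor type.** App periods are the later periods. A drift from research staff to local doctors, or the reverse, would partly align with the intervention.
- **Notice.** A surveyor who knows the date and prescribes on the ward may change practice before the survey.

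**Working it through.** The plan gives no figure for surveyor effects, so the check is mainly textual, followed by an illustration.

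**1. Can a surveyor be a study subject?** Yes for in-patients. The Survey staff list describes a doctor of the surveyed hospital, and the trial measures all prescribers there. No section excludes the surveyor's own ward or own patients.

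**2. Does abstraction need judgement?** To a degree. Form A2 has fields for diagnosis and type of indication and a separate yes/no field for whether a reason is in the notes. This suggests, but does not state, that a diagnosis can be entered when the notes give no reason. Surveyors also classify surgical prophylaxis and look back for ongoing therapy.

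**3. Is there an independent check?** The data management section gives data entry to the principal investigator and trained research staff, and checking to the principal investigator. It describes no second reading of the charts. Entry by research staff does not help if the chart was read by someone else.

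**4. Could surveyor type change with phase?** Nothing prevents it. The model in the statistical analysis section names study arm, duration of exposure and clustering by hospital. It names no term for surveyor or for calendar time, so a drift in surveyor type could load onto the arm effect.

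**5. Illustration of size.** Inputs from Section 3.3 are 30% adherence under paper and a 15% minimum difference, read here as 15 percentage points (45% under the app). Non-adherence N is then 70% with no true effect and 55% in the app phase with the full effect. Two quantities are assumed, because the documents give neither: q, the share of non-adherent records recorded as adherent, and w, the share of app-phase records abstracted by own-ward doctors, with none in the paper phase.

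False gain in points = w × q × N.

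| q (assumed) | w = 1, N = 55 | w = 1, N = 70 |
|---|---|---|
| 2% | 1.1 | 1.4 |
| 5% | 2.75 | 3.5 |
| 10% | 5.5 | 7.0 |

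At q = 5% this is 2.75/15 = 18% to 3.5/15 = 23% of the target difference. With w = 0.25 it falls to 0.25 × 2.75 = 0.69 to 0.25 × 3.5 = 0.88 points.

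**6. The same practice in both phases.** With q = 5% and w = 1 throughout, and a true difference of 15 points, paper is recorded as 30 + 0.05 × 70 = 33.5% and app as 45 + 0.05 × 55 = 47.75%. The recorded difference is 14.25 points, a slight shrinkage. With no true effect, both phases are recorded as 33.5% and there is no false difference. An inflated app effect therefore requires surveyor type or surveyor behaviour to differ between phases.

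**The case against.** The case on the other side is substantial, and much of it stands.

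- **Out-patients.** A reader might infer that the out-patient survey is equally exposed, since its surveyor list also admits local doctors. The text does not support this: research staff enter those data from an image of the prescription. This limits the concern to in-patients.
- **Same-day notice.** A reader might infer that a local surveyor defeats the rule. That goes too far. No section says when the surveyor is told, or why notice is given on the day, and the rule still covers the other ward doctors and nurses. Other notice exists by design. Directors, who are co-investigators, know three days ahead. Rounds recur every four months and may last five working days. Doctors get a week's notice of the guideline, app and training sessions that follow a survey (Appendices A6, A7 and A12).
- **Role of the surveyor.** A reader might suppose that local doctors settle colleagues' unclear handwriting or rate adherence. The Survey setting gives handwriting queries to research staff, and no section says that surveyors rate adherence.
- **Differential behaviour.** All doctors receive the guidelines at month 0, the app has the same content, and the training draws on material already in the guidelines. The app phase therefore gives surveyors no new guideline content, and a phase-linked change of surveyor type is permitted but not planned. This weakens the case for a large bias. It does not remove the opening, because surveyors are unblinded and the training is meant to change awareness.

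How often local doctors will survey is also unknown.

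**Conclusion.** The concern holds for the in-patient survey. The plan lets a prescriber under study abstract primary-endpoint data from a ward where he or she works, and lets surveyor type vary across rounds, with no safeguard against either. The effect on same-day notice is a possible weakening that rests on a reasonable inference: someone due to start at 8:00 would ordinarily be scheduled beforehand.

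The size and even the presence of bias are unknown. The 2.75 to 3.5 points should not be read as an estimate. They rest on an assumed 5% share and on own-ward doctors abstracting every app-phase record and no paper-phase record, out-patients included. Because out-patient data are entered by research staff, that pattern lies at the upper end of what the plan allows. The recommendation rests on the low cost of closing the gap in an unblinded trial with six clusters, and not on a demonstrated distortion.

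**What to change.** - **Eligibility.** Add to the Survey staff list in Section 3.7, a.1 that a local-doctor surveyor may not survey a ward where he or she prescribes.
- **Constancy.** Where feasible, keep the same surveyor type (research staff or outside-ward local doctor) on each ward in all five rounds. This matters more than later adjustment: if every ward changed surveyor type exactly when the app arrived, no analysis could separate the two.
- **Analysis.** Classify surveyor type from the name already on form A1, using a list of surveyors with their role and home ward; no new form field is needed. Repeat the primary analysis with in-patient data restricted to wards surveyed by research staff, or adjusted for surveyor type. Report it as supportive, since surveyor type is not randomised and restriction loses precision.

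The cost is slightly less familiarity with a ward's charts and a small scheduling constraint. It falls hardest on the smallest hospitals. Luang Namtha has 18 physicians and six or seven in-patient wards (Sections 3.2 and 3.7 differ), and doctors may leave during the study. Where no outside-ward doctor is available, research staff can cover the ward.
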